Dizziness Neuropathy: sensory Somnolence/depressed level of consciousness PAIN Pain - Abdomen NOS Pain - Chest/thorax NOS Pain - Head/headache Pain - Pain NOS PULMONARY/UPPER RESPIRATORY Cough Dizziness Neuropathy: sensory Pauropathy: sensory Pain - Abdomen NOS Pain - Abdomen NOS Pain - Head/headache Pain - Head/headache		Confusion		Confusion
Somnolence/depressed level of consciousness PAIN Pain - Abdomen NOS Pain - Chest/thorax NOS Pain - Head/headache Pain - Pain NOS PULMONARY/UPPER RESPIRATORY Cough		Dizziness		
Consciousness PAIN Pain - Abdomen NOS Pain - Abdomen NOS Pain - Abdomen NOS Pain - Head/headache Pain - Pain NOS Pain - Pain NOS Pain - Head/headache Pain - Pain NOS PULMONARY/UPPER RESPIRATORY Cough Coug		Neuropathy: sensory		Neuropathy: sensory
PAIN Pain - Abdomen NOS Pain - Chest/thorax NOS Pain - Head/headache Pain - Pain NOS PULMONARY/UPPER RESPIRATORY Cough				
Pain - Abdomen NOS Pain - Chest/thorax NOS Pain - Head/headache Pain - Pain NOS PULMONARY/UPPER RESPIRATORY Cough		consciousness		
Pain - Chest/thorax NOS Pain - Head/headache Pain - Pain NOS PULMONARY/UPPER RESPIRATORY Cough	PAIN			
Pain - Head/headache Pain - Pain NOS PULMONARY/UPPER RESPIRATORY Cough Pain - Head/headache Pain - Head/headache Pain - Head/headache				Pain - Abdomen NOS
Pain - Pain NOS PULMONARY/UPPER RESPIRATORY Cough				
PULMONARY/UPPER RESPIRATORY Cough				Pain - Head/headache
Cough				
	PULMONARY/UPPE	R RESPIRATORY		
Dyspnea (shortness of breath) Dyspnea (shortness of breath)		Dyspnea (shortness of breath)		Dyspnea (shortness of breath)

RENAL/GENITOURINARY	
Renal/Genitourinary - Other (Renal insufficiency)	Renal/Genitourinary - Other (Renal insufficiency)

This table will be updated as the toxicity profile of the agent is revised. Updates will be distributed to all Principal Investigators at the time of revision. The current version can be obtained by contacting: [contact]. Your name, the name of the investigator, the protocol and the agent should be included in the e-mail.

Also reported on tipifarnib (R115777) trials but with the relationship to tipifarnib (R115777) still undetermined:

ALLERGY/IMMUNOLOGY – Allergic rhinitis (including sneezing, nasal stuffiness, postnasal drip)

BLOOD/BONE MARROW – Blood/Bone Marrow – Other (leukocytosis)

CARDIAC ARRHYTHMIA – Palpitations; Supraventricular and nodal arrhythmia - Atrial fibrillation; Supraventricular and nodal arrhythmia - Sinus tachycardia; Supraventricular and nodal arrhythmia - Supraventricular tachycardia; Ventricular arrhythmia - Ventricular tachycardia

CARDIAC GENERAL – Cardiopulmonary arrest, cause unknown (non-fatal); Left ventricular systolic dysfunction

COAGULATION – PTT (Partial Thromboplastin Time)

CONSTITUTIONAL SYMPTOMS – Rigors/chills; Sweating (diaphoresis); Weight loss **DERMATOLOGY/SKIN** – Dry skin; Hair loss/alopecia (scalp or body); Pruritus/itching **ENDOCRINE** – Hot flashes/flushes

GASTROINTESTINAL – Dry mouth/salivary gland (xerostomia); Flatulence; Gastrointestinal – Other (polydipsia); Ileus, GI (functional obstruction of bowel, i.e., neuroconstipation);

Obstruction, GI - Small bowel NOS; Taste alteration (dysgeusia)

HEMORRHAGE/BLEEDING – Hematoma; Hemorrhage, GI - Oral cavity; Hemorrhage, GI – Upper GI NOS

HEPATOBILIARY/PANCREAS - Liver dysfunction/failure (clinical)

INFECTION - Opportunistic infection associated with >= Grade 2 Lymphopenia

LYMPHATICS – Lymphatics - Other (localized lymphadenopathy)

METABOLIC/LABORATORY – Alkaline phosphatase; ALT, SGPT (serum glutamic pyruvic transaminase); AST,SGOT (serum glutamic oxaloacetic transaminase); Amylase; Calcium, serum-high (hypercalcemia); Glucose, serum-high (hyperglycemia); Magnesium, serum-low (hypomagnesemia); Potassium, serum-high (hyperkalemia); Sodium, serum-low (hyponatremia); Triglyceride, serum-high (hypertriglyceridemia)

MUSCULOSKELETAL/SOFT TISSUE – Muscle weakness, generalized or specific area (not due to neuropathy)

NEUROLOGY – Ataxia (incoordination); Extrapyramidal/involuntary movement/restlessness; Memory impairment; Mood alteration – Agitation; Mood alteration - Anxiety; Mood alteration - Depression; Neuropathy: motor; Psychosis (hallucinations/delusions); Seizure; Syncope (fainting); Tremor

OCULAR/VISUAL – Dry eye syndrome; Ocular/Visual - Other (abnormal vision)

PAIN - Pain - Back; Pain - Bladder; Pain - Bone; Pain - Joint; Pain - Muscle

PULMONARY/UPPER RESPIRATORY – Hiccoughs (hiccups, singulitus); Hypoxia;

Pneumonitis/pulmonary infiltrates; Voice changes/dysarthria (e.g., hoarseness, loss or alteration in voice, laryngitis)

RENAL/GENITOURINARY – Urine color change

VASCULAR – Phlebitis (including superficial thrombosis); Thrombosis/thrombus/embolism

Note: Tipifarnib (R115777) in combination with other agents could cause an exacerbation of any adverse event currently known to be caused by the other agent, or the combination may result in events never previously associated with either agent.

8.2 Drug orders, transfers, returns, Accountability / Emergency Unblinding

Questions about drug orders, transfers, returns, or accountability should be addressed to the PMB by calling [contact] Monday through Friday between 8:30am and 4:30pm Eastern Time.

8.2.1 DRUG ORDERS: No starter supplies will be available for this study. Orkand will notify the PMB (see Section 3.1.2 and Appendix 8A/B) when a patient is registered by the Pediatric Oncology Branch research nurse. Using the "On-Study Form" in Appendix 8B, Orkand will provide the protocol number (i.e., T99-0090), the patient ID / sequence number (e.g., '01C0222-01'), the patient initials (e.g., 'ABC' = first three letters of the patient's last name), and the patient's BSA (in m2). Based on the patient's BSA, the PMB will ship an initial three month patient-specific supply (see table in Section 8.1) for "Phase A" to the registering site.

Two months after the initial request (i.e., one month before needed), clinical sites may reorder an additional three month supply by completing an NCI Clinical Drug Request form and faxing it to the PMB at [contact]. The NCI Clinical Drug Request form is available on the CTEP home page (http://ctep.cancer.gov) or by calling the PMB at [contact]. The patient ID number (e.g., '01C0222-01') and patient initials (e.g., 'ABC') should be entered in the "Patient or Special Code" field. In addition, the patient's BSA must be provided. All drug orders should be shipped directly to the physician responsible for treating the patient.

When the patient progresses on Phase A, the Pediatric Oncology Branch research nurse will notify the PMB (see Section 3.1.2 and Appendix 9A/B). Based on the patient's BSA, the PMB will again ship an initial three month patient-specific supply (see table in Section 8.1) for Phase B to the registering site. Any remaining supplies for Phase A should be returned immediately on receipt of supplies for "Phase B" (see Section 8.2.3).

8.2.2 DRUG TRANSFERS: Boxes MAY NOT be transferred from one patient to another patient or from one protocol to another protocol. All other transfers (e.g., a patient moves from one participating center to another participating center, the principal investigator at a participating center changes, etc) must be approved in advance by the PMB. To obtain an approval for transfer, investigators should complete and submit to the PMB ([contact]) a Transfer Investigational Agent Form available on the CTEP home page http://ctep.cancer.gov, or by calling the PMB at [contact]. The patient ID number (e.g., '01C0222-01') and patient initials (e.g., 'ABC') should be entered in the "Received on NCI Protocol No." and the "Transferred to NCI Protocol No." fields in addition to the protocol number (i.e., T99-0090).

8.2.3 DRUG RETURNS: All unused drug supplies should be returned to the PMB. When it is necessary to return study drug (e.g., sealed boxes remaining when a patient completes the first blinded treatment phase, sealed boxes remaining when a patient completes the second blinded treatment phase, expired boxes recalled by the PMB), investigators should return the study drug to the PMB using the NCI Return Agent Form available on the CTEP home page http://ctep.cancer.gov, or by calling the PMB at [contact]. The patient ID number (e.g., '01C0222-01') and patient initials (e.g., 'ABC') should be entered in the "Lot No. and Sample No." field.

- 8.2.4 DRUG ACCOUNTABILITY: The investigator, or a responsible party designated by the investigator, must maintain a careful record of the receipt, disposition, and return of all drugs received from the PMB using the NCI Investigational Agent Accountability Record available on the CTEP home page http://ctep.cancer.gov, or by calling the PMB at [contact]. A separate NCI Investigational Agent Accountability Record must be maintained for each patient on this protocol. The patient ID number (e.g., '01C0222-01') and the **phase** (i.e., "Phase A" or "Phase B") should be entered in the "Patient's ID No." field.
- 8.2.5 EMERGENCY UNBLINDING: In the event of an emergency, call [name] [contact]) or [name] [contact]). These physicians can also be reached through [contact] or through the NIH Page Operator at [contact]. Pediatric Oncology Branch staff will require the protocol number (i.e., T99-0090), the patient ID number (e.g., '01C0222-01), the patient initials (e.g., 'ABC'), and the phase (i.e., 'Phase A' or 'Phase B') to unblind the patient.

9.0 CLINICAL TRIALS AGREEMENT (CTA)

The agent(s) (hereinafter referred to as "Agent", R115777, used in this protocol is/are provided to the NCI under a Clinical Trials Agreement (CTA) between Company: Janssen Pharmaceuticals (hereinafter referred to as "Collaborator(s)") and the NCI Division of Cancer Treatment, Diagnosis. Therefore the following obligations/guidelines apply to the Agent(s) in this study:

- 1) The Agent(s) may not be used outside the scope of this protocol, nor can the Agent(s) be transferred or licensed to any party not participating in the clinical study. Collaborator(s) data for Agent(s) are confidential and proprietary to the Collaborator(s) and should be maintained as such by the investigators.
- 2) For a clinical protocol where there is an investigational Agent used in combination with other investigational Agent(s), each the subject of different CTAs, the access to and use of data by each Collaborator shall be as follows (data pertaining to such combination use shall hereinafter be referred to as "Multi-Party Data").
 - a) NCI must provide all Collaborators with written notice regarding the existence and nature of any agreements governing their collaboration with NIH, the design of the proposed combination protocol, and the existence of any obligations which would tend to restrict NCI's participation in the proposed combination protocol.

b) Each Collaborator shall agree to permit use of the Multi-Party Data from the clinical trial by any other Collaborator to the extent necessary to allow said other Collaborator to develop, obtain regulatory approval or commercialize its own investigational Agent.

- c) Any Collaborator having the right to use the Multi-Party Data from these trials must agree in writing prior to the commencement of the trials that it will use the Multi-Party Data solely for development, regulatory approval, and commercialization of its own investigational Agent.
- 3) The NCI encourages investigators to make data from these clinical trials fully available to Collaborators for review at the appropriate time. Clinical trial data developed under the CTA will be made available exclusively to Collaborator(s), the NCI, and the FDA, as appropriate.
- 4) When a Collaborator wishes to initiate a data request, the request should first be sent to the NCI, who will then notify the appropriate investigators (Group Chair for cooperative group studies, or PI for other studies) of Collaborator's wish to contact them.
- 5) Any data provided to Collaborator(s) must be in accordance with the guidelines and policies of the responsible Data Monitoring Committee (DMC), if there is a DMC for this clinical trial.
- 6) Any manuscripts reporting the results of this clinical trial should be provided to CTEP for immediate delivery to Collaborator(s) for advisory review and comment prior to submission of publication. Collaborator(s) will have 30 days from the date of receipt for review. An additional 30 days may be requested in order to ensure that confidential and proprietary data, in addition to Collaborator(s) intellectual property rights, are protected. Copies of abstracts should be provided to Collaborator(s) for courtesy review following submission, but prior to presentation at the meeting or publication in the proceedings. Copies of any manuscript and/or abstract should be

sent to: Regulatory Affairs Branch, CTEP, DCTD, NCI

[name]

Bethesda, MD 20892

[contact]

The Regulatory Affairs Branch will then distribute them to Collaborator(s).

11.0 APPENDICES

APPENDIX 1: PROTOCOL FOR REQUIRED PRE STUDY AND ON STUDY MRI STUDIES

Prior to starting treatment on this study all known measurable tumors should be imaged with MRI to obtain a baseline. Tumor spread in patients with NF1 can be very extensive, and may not allow for all lesions to be followed using 3D-MRI.

The goal will therefore be to use 3D-MRI only to follow the progressing plexiform neurofibroma(s) (a maximum of three lesions), which will be defined as index lesion(s).

Pre-study radiographic evaluation:

- Identify and select the progressive plexiform neurofibroma(s) (a maximum of three lesions) for 3-D MRI evaluation based on prior imaging studies. Should there be more than 3 progressing plexiform neurofibromas, the three most clinically relevant plexiform neurofibromas will be followed by 3-D MRI analysis.
- Perform 3-D MRI sequences on the selected index lesions as outlined in the MRI acquisition protocols below.
- In addition, if possible, perform MRI of all additional measurable plexiform neurofibroma(s).

On study radiographic evaluation:

Unless clinically indicated otherwise obtain MRI of the index lesions only as outlined in the MRI acquisition protocol below prior to cycles 4, 7, 10, and then after every 6 cycles on each treatment phase ("A", "B").

At the time of disease progression on treatment phase "A",if possible, a MRI scan of all known measurable plexiform neurofibromas in addition to the index lesions should be performed, in order to have a new baseline prior to treatment phase "B".

MRI protocols:

Depending on the location of the index lesions the Spine, Head/Neck or Trunk/Extremities protocols outlined on the following pages will be used.

The measurement of very irregular or infiltrative neurofibromas will present major challenges, and in some cases, it may be difficult to precisely define tumor margins. If necessary, participating institutions may modify the MRI sequences to optimize differentiation of tumor and surrounding tissue. Modifications should be documented in the MRI protocols, and the same imaging protocol, and, if possible, the same MRI scanner, should be used for all subsequent MRI studies.

Every attempt should be made to image the entire progressive plexiform neurofibroma(s).

A written protocol for scanning each patient has to be established at the time of study entry to allow for reproducibility of follow-up studies.

If possible, [name] should be notified at least 24 hours prior to performing a MRI ([contact], [contact], e-mail: [contact]).

A copy of the MRI protocol used to acquire the baseline MRI study will be faxed to [name] [contact]) within 24 hours of obtaining the MRI study.

MRI studies should be submitted electronically or on CD or optical disk to the NCI POB within 1 week of obtaining the study. The institutional radiology report for each study should be faxed to [name] within 1 week.

MRI PROTOCOL- SPINE

Patient ID	number	
	111111111111111111111111111111111111111	

Note: All series except for #4 and #5 should be performed as a normal clinical scan as specified by the radiologist. The additional Series #4 and #5 may or may not be part of the normal clinical scan sequence, however these series are required for the NF1 study protocol and must be performed within protocol specifications as indicated below.

SAGITTAL T1 LOCALIZER—SPINE COIL Per normal clinical scan
 SAGITTAL T1 Per normal clinical scan
 SAGITTAL FSEIR Per normal clinical scan

4. AXIAL FSEIR

Axial FSEIR	Protocol	Actual	Reason For Change
	Specifications	Specifications	
Echo Train Length	5		
TR	6000		
TE	34		
TI	150		
Slice Thickness	5 mm		
Skip	0		
Matrix	256x256		
FOV	22 cm		
NEX	1		
Frequency Direction	R→L		
Options	Tailored RF, FC, PC, 0.7	75 FOV	

5. CORONAL FSEIR

Coronal FSEIR	Protocol	Actual	Reason For Change
	Specifications	Specifications	
Echo Train Length	5		
TR	6000		
TE	34		
TI	150		
Slice Thickness	5 mm		
Skip	0		
Matrix	256x256		
FOV	22 cm		
NEX	1		
Frequency Direction	S→I		
Options	Tailored RF, FC, PC		

6.	AXIAL T1	Per normal clinical scan
7.	AXIAL T1- POST CONTRAST	Per normal clinical scan
Date:	Signature (responsible MRI technician):	

Baseline study only, fax completed form to: [name] at: [contact] ([contact])

4/21/2009	T-99-0090, 01-C-0222
-----------	----------------------

MRI Protocol- Head/Neck

Patient ID number:	PATI	ENT ID NI	IMBER:	
--------------------	------	-----------	--------	--

Note: All series except for #2 and #3 should be performed as a normal clinical scan as specified by the radiologist. The additional Series #2 and #3 may or may not be part of the normal clinical scan sequence, however these series are required for the NF1 study protocol and must be performed within protocol specifications as indicated below.

1. SAGITTAL T1

Per normal clinical scan

2. AXIAL FSEIR

Axial FSEIR	Protocol	Actual	Reason For Change
	Specifications	Specifications	
Echo Train Length	5		
TR	6000		
TE	34		
TI	150		
Slice Thickness	4 mm		
Skip	0		
Matrix	256x256		
FOV	22 cm		
NEX	1		
Frequency Direction	A→P		
Options	Tailored RF, FC, 0.75 FC	OV	

3. CORONAL FSEIR

Coronal FSEIR	Protocol	Actual	Reason For Change
	Specifications	Specifications	
Echo Train Length	5		
TR	6000		
TE	34		
TI	150		
Slice Thickness	5 mm		
Skip	0 mm		
Matrix	256x192		
FOV	22 cm		
NEX	1		
Frequency Direction	S→I		
Options	Tailored RF, PC		

4.	AXIAL T1	Per normal clinical scan
5.	AXIAL T1- POST CONTRAST	Per normal clinical scan
Date:_	Signature (responsible MRI technician):	

Baseline study only, fax completed form to: [name] at: [contact] ([contact])

4/	21	/2009	T-99-0090, 01-C-0222
-,		/ ====	,

MRI Protocol-Trunk/Extremities

PATIENT ID	NUMBER:

Note: All series except for #1 and # 2 should be performed as a normal clinical scan as specified by the radiologist. The additional Series #1 and # 2 may or may not be part of the normal clinical scan sequence, however these series are required for the NF1 study protocol and must be performed within protocol specifications as indicated below.

1. AXIAL PLANE-STIR

Axial Plane STIR	Protocol	Actual	Reason For Change
	Specifications	Specifications	
Coil: Body			
Sequence: Fast Spin Ecl	ho (Turbo) FSEIR		
Echo Train Length	5		
TR	6000		
TE	TE 15		
TI	150		
Slice Thickness	10 mm		
Skip	0		
Matrix	512x160		
FOV	40x30		
No. of Excitations/ Sequence	0.5		
No. of Acquisitions	1		
Saturation	None		

2. CORONAL PLANE STIR

Coronal Plane STIR	Protocol	Actual	Reason For Change
Specifications		Specifications	
Coil: Body			
Sequence: Fast Spin Ec	ho (Turbo) FSEIR		
Echo Train Length	5		
TR	3400		
TE	15		
TI	150		
Slice Thickness	5 mm		
Skip	0		
Matrix	512x160		
FOV	48x48		
No. of Excitations/ Sequence	1		
No. of Acquisitions	1		
Saturation	None		

Date:	Signature	responsible MRI techniciar	ı):
	0	\ 1	/

Baseline study only, fax completed form to: [name] at: [contact] ([contact])

Data Analysis:

• All MRI data will be analyzed at the Pediatric Oncology Branch of the NCI under guidance of Dr. [name] (head neuroradiologist). The MRI data from each scan will be processed to assess the volume of the index plexiform neurofibroma(s). The tumor will be traced on subsequent contiguous MR slices, the numbers summed and then multiplied by the slice thickness to obtain a numerical volume measurement. The tumor will be identified by high signal on the T2 images not corresponding to known normal anatomic structures and corresponding with the course of known nerves. Each patient's volumetric measurement obtained from the initial MRI will serve as the baseline against which to assess incremental changes in volume that occur during the subsequent intervals. Volumetric measurements and 1D-, and 2D-data analysis will be done by 2 physicians trained in 1D-, 2D-, and 3D-MRI data analysis at the Pediatric Oncology Branch, NCI at an Image Review Workstation using MEDx software (Sensor Systems Inc.). [name], NCI, will review and confirm 1D-, 2D-, and volumetric measurements for all images obtained on the study. Volumetric measurements will be used to determine disease progression as outlined in Section 5.2. After review by [name], the Principal Investigator will inform the Participating Investigators about the results of the MRI study by written report.

• The results of volumetric MRI measurements will be compared with 1D- and 2D-MRI measurements, with results of the photographic evaluation, the physical examination and the study subject's subjective impression following clinical variables.

Image And Data Acquisition:

In order to perform quantitative analysis the Pediatric Oncology Branch must receive the imaging data from the investigator sites.

Distribution of images from all participating institutions to the NCI POB will be performed by a contractor.

The contractor will:

- Contact participating institutions to determine the best mode of electronic data transfer
- Prepare each site for electronic data transfer via network access device, File Transfer Protocol (ftp), optical disk or modem depending on the investigator site.
- Provide training and technical support for each site
- Ensure complete, secure and timely data transfer to the POB, NCI within 24-72 hours of obtaining the MRI study.

The Pediatric Oncology Branch will check all materials received for completeness and will notify the site if data, images, or information are missing or incomplete.

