3.1.5 Definition of Tumor Progression

- A ≥ 20% increase in the volume (by 3D-MRI) of at least one of the index plexiform neurofibromas compared to the pretreatment volume measured prior to the start of the current treatment phase.
- Appearance of new discrete dermal neurofibroma(s) does not qualify for disease progression.
- Worsening of existing symptoms or the appearance of new symptoms that persist for more than 7 days and that are felt to be definitely related to plexiform neurofibroma should be evaluated by repeating the MRI. Patients should not be classified as having progressive disease solely on the basis of new or increased symptoms without discussing the case with the protocol Principal Investigator.
- Patients with other evidence of disease progression than outlined above should also be discussed with the Principal Investigator.

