3.4.4 RADIOGRAPHIC EVALUATION: Evaluate the index lesions by MRI prior to cycle 1 on treatment phase "A", and prior to cycle 4, 7, 10, and then after every 6 cycles on each treatment phase ("A", "B"). The protocol outlined in Appendix 1 will be used each

time MRI examinations are performed to assess progression or response to R115777 or placebo. In patients with clinical suspicion of disease progression MRI analysis should be performed earlier using the protocol outlined in Appendix 1. At the time of disease progression on treatment phase "A", if possible, a MRI scan of all known measurable plexiform neurofibromas in addition to the index lesions should be performed, in order to have a new baseline prior to treatment phase "B" (Appendix 1).

- 3.4.5 OPHTHALMOLOGIC EVALUATION: Prior to or within the first three days of starting treatment phase "A", and prior to or within the first 3 weeks of starting treatment phase "B". Exam should include visual fields if the patient is able to cooperate with the exam and examination of the lens for opacifications.
- 3.4.6 TISSUE PROCUREMENT: In patients with easily accessible discrete neurofibromas or superficial plexiform neurofibromas, who consent to the procedure, biopsies will be performed prior to the first dose of treatment on phase "A", and if feasible at one steady state time point on each treatment phase ("A", "B") (between day 15-21 on cycle #1) of treatment. In addition, attempts will be made to obtain tumor specimens from any patients requiring surgery for complications of their tumors or for unrelated medical problems. Peripheral blood mononuclear cells for FPTase assay (Section 3.4.7, appendix 5) should be obtained at the same time as biopsy whenever possible. As this is an invasive procedure, patients may refuse biopsy and still be eligible for the study.

Two kits will be supplied for handling and shipping of tumor specimens. To obtain the kits, please call [name] [contact]. Kits will be sent by FedEx to arrive several days prior to the surgical procedure. Included in the kits will be all media and tubes needed for shipment. Procedures for tissue handling and shipment are provided in Appendices 3 and 4, respectively.

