5.2 RESPONSE CRITERIA

Response is assessed at the time that follow-up 3D-MRI scans are performed (prior to cycles 4, 7, 10, then q6 cycles). For the purpose of determining the level of response (complete, partial, minor, etc.) measurements from the follow-up scans are compared to the tumor size in the pretreatment MRI scan using 3D data analysis. Response determined using 3D-MRI volumetric analysis will be compared with 2D- and 1D-MRI measurements.

COMPLETE RESPONSE (CR): A complete resolution of all measurable or palpable soft tissue tumors for ≥ 4 weeks and no appearance of new lesions.

PARTIAL RESPONSE (PR): A \geq 50% reduction in the sum of the volume of all index lesions for \geq 4 weeks.

MINOR RESPONSE (MR): A \geq 25% but <50% reduction in the sum of the volume of all index lesions for \geq 4 weeks.

STABLE DISEASE (SD): A <20% increase, and < 25% decrease in the sum of the volume of all index lesions for ≥4 weeks.

PROGRESSIVE DISEASE (PD):

 A ≥ 20% increase in the volume (by 3D-MRI) of at least one of the index plexiform neurofibromas compared to the pretreatment volume measured prior to the start of the current treatment phase.

- The appearance of new discrete subcutaneous neurofibromas does not qualify for disease progression.
- Worsening of existing symptoms or the appearance of new symptoms that persist
 for more than 7 days and that are felt to be definitely related to the plexiform
 neurofibroma should be evaluated by repeating the MRI. Patients should not be
 classified as having progressive disease solely on the basis of new or increased
 symptoms without discussing the case with the protocol Principal Investigator.
- Patients with other evidence of disease progression than outlined above should also be discussed with the Principal Investigator.

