APPENDIX 7: REQUIRED STUDY EVALUATIONS

Prior To Starting Treatment, During, And Post Treatment for Each Study Phase ("A" and "B"):

Observation	Pretreatment (Phase A&B)	During Cycle (Phase A&B)	Prior to Each Cycle (Phase A&B)	Post Study
History & physical exam	X	q 2 weeks, Cycles 1-3	Χ	Χ
Performance status	X		X (document if changed)	X
Body surface area	X		X	
Photography of lesions, if	X		Cycles 4, 7, 10, then q 6 cycles	Χ
possible				
CBC, platelets, differential	X	q 2 weeks, Cycles 1-3	X	X
PT, PTT, Fibrinogen	X		X	Χ
Electrolytes and creatinine	X	q 2 weeks, Cycles 1-3	X	Χ
Ca ⁺² , Mg ⁺² , PO ₄	X	q 2 weeks, Cycles 1-3	X	Χ
SGPT, bilirubin	X	q 2 weeks, Cycles 1-3	X	Χ
Urinalysis	X		Cycles 4, 7, 10, then q 6 cycles	Χ
Urine pregnancy test	Females			
3D-MRI of index lesions	Phase A only		Cycles 4, 7, 10, then q 6 cycles	Χ
Ophthalmologic examination	X			Χ
QOL assessment	Phase A only		Cycles 4, 7, 10, then q 6 cycles	
Tumor Biopsy	Phase A only	Between days 15-21, Cycle 1 Phase A and B		
PBMC for FPTase	Phase A only	Between days 15-21, Cycle 1		

Nerve growth factor Phase A only

Cycles 4, 7, 10, then q 6 cycles

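### Appendix 1 takes the initial MRI as the volume baseline and Section 5.2 names no phase for response, so response to R115777 in placebo-first patients could be understated

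*Combined protocol and SAP*

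**What the plan says.** **Baseline for volume change.** The Data Analysis part of Appendix 1, which describes the central MRI reading, states that each patient's "volumetric measurement obtained from the initial MRI will serve as the baseline against which to assess incremental changes in volume". It names no treatment phase. The same paragraph adds: "Volumetric measurements will be used to determine disease progression as outlined in Section 5.2".

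**Progression.** Sections 3.1.5 and 5.2 both require growth of at least 20% in at least one index lesion, "compared to the pretreatment volume measured prior to the start of the current treatment phase".

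**Response.** For the level of response, Section 5.2 says that "measurements from the follow-up scans are compared to the tumor size in the pretreatment MRI scan using 3D data analysis". No phase is given. Partial response (PR) is a fall of at least 50% in summed index volume. Minor response (MR) is at least a "25% but <50% reduction in the sum of the volume of all index lesions". Stable disease (SD) is less than a 20% increase and less than a 25% decrease in the same sum.

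**Phase B baseline scan.** Section 1.2.8 calls for imaging before entry to each phase. Section 3.1.4 schedules MRI before cycle 1 on each phase, and Section 3.1.1 resets the cycle count at crossover. Section 3.4.4, however, names the pre-cycle-1 scan for phase A only. In Appendix 7 the row "3D-MRI of index lesions" is marked phase A only, in a pretreatment column headed for both phases. Section 3.4.4 and Appendix 1 also ask, where possible, for a wider scan at phase A progression "in order to have a new baseline prior to treatment phase" B.

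**The concern.** In phase A the initial MRI and the phase baseline are the same scan, so the wording does no harm. In phase B they differ, usually by at least the growth that triggered crossover. The deferral in Appendix 1 covers progression only. For response, a central reader has a patient-level rule in Appendix 1, an unqualified reference in Section 5.2, and two schedules that list no separate pretreatment index-lesion scan for phase B.

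Objective 1.1.2, the response rate to R115777, is listed as primary. Thirty of the 60 planned patients are randomised to placebo first, and they receive R115777 only in phase B, after progression. If their shrinkage is counted from the initial scan, they must first undo the growth that occurred on placebo. The same criterion is then harder to meet in phase B than in phase A, and the error runs against R115777.

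**Working it through.** **1. The plan's own figure.** Section 5.4.2 gives 30 per arm for median time to progression of 6 vs. 12 months, one-sided alpha 0.05, power 80%, with 36 months of accrual and 12 of follow-up.

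- Events (Schoenfeld): 4 × (1.645 + 0.842)² / (ln 0.5)² = 51.5, rounded up to 52.
- Probability of an event, exponential times and uniform accrual: 1 − [exp(−12λ) − exp(−48λ)] / (36λ), with λ = ln 2 / median. This gives 0.941 (placebo) and 0.790 (R115777), mean 0.865.
- N = 52 / 0.865 = 60.1, which matches 60. Power at N = 60 (51.9 events) is 0.803.

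This calculation uses the first period only, where the initial MRI is the phase baseline. The baseline conflict does not touch it.

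**2. Thresholds in phase B if the initial MRI is the response baseline.** Let g be total index volume at the start of phase B divided by initial total volume. The fall needed during phase B is 1 − 0.50/g for PR and 1 − 0.75/g for MR. A true 50% fall ends at 0.50g of initial volume, and a true 25% fall at 0.75g.

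The documents give no distribution for g, so the values below are assumptions. For a patient with one index lesion who crosses over on the volume criterion, 1.20 is the minimum. With one of three equal lesions up 20%, g = (1.2 + 1 + 1)/3 = 1.067.

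| g | Fall needed for PR | Fall needed for MR | True 50% fall, against initial | True 25% fall, against initial |
|---|---|---|---|---|
| 1.067 | 53.1% | 29.7% | 46.7% below: MR | 20.0% below: SD |
| 1.20 | 58.3% | 37.5% | 40.0% below: MR | 10.0% below: SD |
| 1.30 | 61.5% | 42.3% | 35.0% below: MR | 2.5% below: SD |
| 1.40 | 64.3% | 46.4% | 30.0% below: MR | 5.0% above: SD |

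In every row a shrinkage of exactly 50% on R115777 drops from PR to MR, and one of exactly 25% drops from MR to SD.

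**3. Coherence of the categories.** Take one index lesion at 1.20 times initial volume at crossover, with no growth in phase B. Against the phase B starting volume the change is 0%, so it is not progression. Against the initial scan it is +20%, which is not below 20%, so it is not SD. It is not a response either. With progression reset by phase and response tied to the initial scan, this patient has no category.

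**The case against.** The best defence is that Section 5.2 explains its own term. Its progression bullet ties the pretreatment volume to the start of the current phase, so the pretreatment scan in the response sentence can be read the same way. SD and progression share the 20% boundary, and only a common baseline makes them fit together, as step 3 shows. The phase A only entry in Appendix 7 is compatible with the phase A progression scan serving as the phase B baseline, and Appendix 1 itself describes a scan that "should be performed, in order to have a new baseline prior to treatment phase" B.

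This stands as the sensible reading, and it makes the understatement conditional. It does not remove the conflict: no sentence applies the phase-specific baseline to response, and the baseline sentence in Appendix 1 says otherwise.

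A reader might infer more: that a lesion already at 120% of initial volume would count as progressed at its first phase B scan, making phase B progression automatic and ruining the second-period and paired comparisons. The documents do not support this. Both progression definitions reset the baseline, Appendix 1 defers to Section 5.2 for progression, and a phase B baseline scan is described in Sections 1.2.8, 3.1.4 and 3.4.4 and in Appendix 1. For the same reason the phase A scan is not the only baseline named.

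Nor is it certain that every patient enters phase B at least 20% above the initial scan. Symptomatic or other progression may be accepted after discussion with the Principal Investigator, and Appendix 9A has a line for clinical progression, although Section 3.6.3 refers to 3D-MRI documentation. The share of R115777 exposure falling in phase B cannot be derived, because it depends on unknown progression times.

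**Conclusion.** The concern holds for response. The plan states two different baselines for volume change, and the cross-reference settles only progression. Using the initial MRI in phase B would raise the PR threshold from 50% to 58.3% and the MR threshold from 25% to 37.5% when total index volume at crossover is 1.20 times initial. The thresholds would be 53.1% and 29.7% if one of three equal lesions grew 20%, and higher if growth at crossover exceeds 20%. These figures rest on assumed crossover volumes and on the initial scan actually being used. The effect on the overall response rate cannot be calculated, because neither the number of placebo-first patients who reach phase B nor their volumes are given.

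The primary phase A comparison, its sample size and its power are unaffected. Since response rate is a listed primary objective and the correction is simple, the text should be changed.

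**What to change.** 1. In Appendix 1 (Data Analysis) and in the response sentence of Section 5.2, state one rule: all categories (complete, partial and minor response, stable and progressive disease) are measured from the last MRI before the start of the current treatment phase. For phase B this is the MRI documenting phase A progression.
2. Reconcile Section 3.4.4 and Appendix 7 with Sections 1.2.8 and 3.1.4 on the phase B baseline scan of the index lesions.

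The cost is two sentences and two schedule entries. The progression definition, sample size and primary analysis stay as they are. Generally no extra scan is needed: crossover already calls for MRI documentation, and Section 3.1.4 asks for a repeat scan at clinical progression if none was done in the past 4 weeks.
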